### 3.3 Impact estimates

The main analysis of impacts will be performed using intent-to-treat (ITT) specifications, wherein all study participants in the originally assigned program group at baseline are included in the statistical analysis and analyzed according to their program group, regardless of whether they received interventions or not. Respondents who refused or withdrew consent or those who are ineligible according to study protocol are excluded from ITT analysis.

The main impacts of the interventions will be estimated for: (1) dietary diversity score, (2) consumption of unhealthy foods/junk foods, and (3) meal frequency. Secondarily, impact will be estimated for exposure to the core interventions: classroom lessons about adolescent nutrition and healthy diets, flag ceremonies/assemblies to remind about key healthy eating messages, adolescent girls club/student peer mentoring on adolescent nutrition, and parent-teacher meetings to educate parents about adolescent nutrition and healthy diets. All impact indicators will be assessed among adolescent girls, except for the exposure to parent-teacher meetings which will be assessed from parents.

Given that the main impact indicators with full sample sizes were collected at endline only, linear regression models will be used to test the means of the outcome for estimates of group differences (intervention vs. control) at endline, with standard errors clustered at the school level. In the adjusted models, we will control for covariates such as adolescent girl age and other variables that differed between study arms. Robustness tests will be conducted using difference-in-differences analysis where outcome variables exist at baseline.

Table 6. Dummy table for impact estimates

Indicator	Baseline		Endline		Unadjusted impact est. 	Adjusted impact est. 
	A&T (N=)	Control (N=)	A&T (N=)	Control (N=)		
	Percent/Mean (SD)	Percent/Mean (SD)	Percent/Mean (SD)	Percent/Mean (SD)		
Dietary diversity score						
Consumption of unhealthy foods						
Meal frequency						

Controlling for clusters by school only.

Adjusted for AG age, household food security and wealth tertile, and clustered by school.

\*\*\* p<0.01; \*\* p<0.05; \* p<0.1

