## III. Methods: Assignment of Interventions

### 3.1 Allocation

A cluster is defined as the primary school that includes grades 1-8. Four woredas in SNNPR (with 31 schools) and three woredas in Somali region (with 23 schools), i.e., one school under each woreda school supervisor, were selected as potential intervention areas (see **Figure 3**). (Within woredas, there are designated supervisors at the education office who are responsible for supervising 1-7 schools. Supervisors are responsible for visiting schools one day per week (less frequently in the Somali region) and are provided with a checklist to ensure that schools are operating effectively. As feasible, we tried to select one school under the responsibility of a (unique) supervisor, to avoid study contamination and confusion among supervisors in conducting their duties.) The samples across the two regions will be pooled to estimate effects at program level. We will use stratified randomization within woreda to try to balance potential co-interventions and confounders. Then 27 schools will be allocated to the intervention arm and 27 schools will be allocated to the control arm by use of computer-generated pseudo-random numbers.

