#### 4.1.4 Adolescent girl questionnaire

Interviews with adolescent girls will be conducted at baseline and endline and gather information on school attendance, exposure to nutrition information, dietary diversity, meal and snacking habits, WASH practices, health and health seeking behaviors, health and nutrition knowledge, food security, home food environment, parental interactions, social desirability, gender and marriage beliefs and decision-making power, and anthropometry.

Table 8. Description of modules in the adolescent girl questionnaire

Module	Topic	Description	Respondent
1	Identification	School and grade of adolescent	Enumerator
2	Adolescent and family background	Age, DOB, grade level, language, characteristics of mother/father	Adolescent
3	School attendance	Attendance, reasons for absences, extracurricular activities, class performance	Adolescent
4	Exposure to nutrition information	Exposure to adolescent nutrition and/or WASH information at school and outside of school, and exposure to media and food/drink advertisements	Adolescent
5	Dietary diversity	Dietary diversity of the adolescent in the past 24 hours	Adolescent
6	Meal and snacking habits	Meals/snacks taken during school days, foods consumed before and during school, access to food vendors near school grounds	Adolescent
7	WASH practices	Handwashing, drinking water, food hygiene, menstruation	Adolescent
8	Health and health seeking behaviors	Illness, health seeking behaviors, weight and body image	Adolescent
9	Health and nutrition knowledge	General knowledge of health and nutrition, including WASH and importance of various macro and micronutrients	Adolescent
10	Home food environment	Availability of foods at home	Adolescent

11	Food security	Prevalence of household hunger using the FANTA household food insecurity access scale (HFIAS)	Adolescent
12	Parent-adolescent interactions	Relationship and interactions with parents, and perceptions of parents' monitoring of food and eating habits	Adolescent
13	Social desirability	Desire for social approval	Adolescent
14	Gender, marriage beliefs and decision-making power	Opinions about girls' and boys' education, marriage and household roles, and decision-making power in the household	Adolescent
15	Anthropometry	Weight and height measurements	Adolescent

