#### 4.1.5 Parent questionnaire

Interviews with parents of adolescent girls will be conducted at baseline and endline and gather information on school involvement, exposure to nutrition information, dietary diversity, health and nutrition knowledge, food security, home food environment, social desirability, gender and marriage beliefs and decision-making power, dwelling and assets.

Table 9. Description of modules in the adolescent girls' parents' questionnaire

Module	Topic	Description	Respondent
1	Identification	School and respondent type	Enumerator
2	Household roster	Information on composition of the household, including designation of the head of household, a list of all household members, their ages and sex, and their relationship to the adolescent girl, and the highest educational level attained and activity/employment in the past month of all household members at least 15 years of age	Parent
3	School involvement	School fees, and participation in parent-teacher association, school management committee and teacher meetings	Parent
4	Exposure to nutrition information	Exposure to adolescent nutrition and/or WASH information, and exposure to media and food/drink advertisements	Parent
5	Dietary diversity	Dietary diversity of the adolescent and household in the past 24 hours	Parent
6	Home food environment	Availability of foods at home	Parent
7	Health and nutrition knowledge	General knowledge of health and nutrition, including WASH and	Parent

		importance of various macro and micronutrients	
8	Parent-adolescent interactions	Relationship and interactions with adolescent, monitoring of food and eating habits, adolescent weight and body image	Parent
9	Social desirability	Desire for social approval	Parent
10	Gender, marriage beliefs and decision-making power	Opinions about girls' and boys' education, marriage and household roles, and decision-making power in the household	Parent
11	Food security	Prevalence of household hunger using the FANTA household food insecurity access scale (HFIAS)	Parent
12	Dwelling	House construction (materials used for floor, walls, and roof), availability of water and electricity, sources of fuel/energy for cooking, WASH facilities	Parent
13	Assets	Ownership of durable household goods (in working condition), including tools for agricultural production	Parent

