## 1.2 Impact evaluation study design

The impact evaluation of A&T's interventions used a cluster-randomized design with repeated cross-sectional surveys at baseline and endline. We applied stratified random allocation to 54 primary schools within 7 districts (*woredas*) across two regions (SNNP and Somali), which were assigned to either the A&T intervention schools (27 schools) or control schools (27 schools). A small baseline survey was conducted in October-November 2019, and the endline survey was conducted in March-May 2021 in the same 54 schools, thereby creating panel data at the school level (not at individual level). Program implementation duration was approximately 4 months (1 school semester); implementation faced major disruptions due to the COVID-19 pandemic throughout most of 2020, with state lockdown/restrictions and school closures, until schools reopened in October 2020.

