## II. Outcome Measures and Indicators

Outcome measures corresponding to the three research questions are presented below. Outcome measures under RQ 1 includes the primary outcome of the evaluation (i.e., used to test study hypotheses and arrive at a decision on overall study impact and to serve as basis to calculate the sample size); RQs 2 and 3 focus on secondary outcomes.

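### SAP 3.3 describes the adjusted impact model in two unreconciled ways, names neither Table 6 column as deciding, and leaves out the woreda strata

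*SAP*

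**What the plan says.** SAP 3.3 makes an endline linear regression with school-clustered standard errors the main analysis, and difference-in-differences a robustness test. Three places bear on which regression is meant.

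- The text: "we will control for covariates such as adolescent girl age and other variables that differed between study arms". The list is open-ended. It gives no candidates, no criterion for a difference and no survey round.
- Table 6, footnote 2: "Adjusted for AG age, household food security and wealth tertile, and clustered by school". This list is closed.
- Table 6, footnote 1, for the unadjusted column: "Controlling for clusters by school only".

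SAP II says that the primary outcome, the dietary diversity score, is "used to test study hypotheses and arrive at a decision on overall study impact". No sentence says which Table 6 column delivers that decision.

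On randomisation, SAP 1.2 says "We applied stratified random allocation to 54 primary schools within 7 districts", and Protocol 3.1 says "We will use stratified randomization within woreda to try to balance potential co-interventions and confounders". Woreda appears in neither the text rule nor the footnotes. Protocol 4.4 does not settle the matter: it speaks generally of controlling for differences and allows difference-in-differences, ANCOVA or both, with unnamed covariates.

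**The concern.** With two definitions of the adjusted model and two unranked columns, at least three estimates could be reported as the trial's result: unadjusted, text rule and footnote list. The trial is unblinded (Protocol 3.2). If arm differences are judged on endline data, the model is settled only once the outcome data exist. If they are judged on baseline data, the list could have been fixed in early 2020, when Protocol 7.1 schedules the baseline results. The documents do not say which.

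At stake is room to choose among estimates, and a disputed verdict when the effect is moderate. The missing stratum is a separate matter. If diets differ strongly between woredas, a model without woreda carries that variation in its standard error although the design has balanced it, and power is lost.

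**Working it through.** **1. The plan's own figure.** None of these clauses carries a number, but the design inputs can be checked. Protocol 2.6 gives SD 1.40, difference 0.6, ICC 0.18, 80% power and 27 schools per arm. Two-sided at 5%:

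n0 = 2 × (1.960 + 0.842)² × 1.40² / 0.6² = 85.47

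n = n0(1 − ICC)k / (k − n0 × ICC) = 85.47 × 0.82 × 27 / (27 − 15.38) = 162.9

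That is 6.03 girls per school, rounded up to 7, and 7 × 27 = 189, as stated. Below I use the endline design (54 schools, 10 girls each), the updated SD of 1.56, and both ICCs in Protocol 2.6 (0.18 and 0.015).

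**2. What the text rule could select.** SAP 3.2 lists 11 characteristics, 10 besides girl age. If each were tested independently at 5% (an assumption), at least one would differ by chance with probability 1 − 0.95^10 = 40%. A t-test that ignores clustering flags a balanced covariate with probability f = 2[1 − Φ(1.96/√(1 + 9 × ICC))]: 6.6%, 10.4% and 22.6% at covariate ICCs of 0.015, 0.05 and 0.18. The chance of flagging exactly food security and wealth is f²(1 − f)^8: 0.45% at f = 0.104 and 0.66% at f = 0.226. Under such a rule, text and footnote would rarely coincide by chance.

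**3. Simulation.** Each scenario had 8,000 null trials, with 27 v 27 schools stratified by woreda. Assumed inputs: 11 covariates with joint R² 10%; covariate ICC 0.18 (A, B) or 0.05 (C, D); text rule read as a 5% t-test at endline; school counts per woreda 8,8,8,7 and 8,8,7, since the documents give only 31 and 23 by region. Monte Carlo error is about 0.25 points at 5%.

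| | A | B | C | D |
|---|---|---|---|---|
| Outcome ICC | 0.18 | 0.18 | 0.015 | 0.015 |
| Share of clustering between woredas | 0 | 0.5 | 0 | 0.5 |
| Null rejection %, unadjusted | 4.9 | 2.4 | 5.3 | 4.9 |
| Text rule | 4.7 | 2.5 | 4.9 | 4.5 |
| Footnote list | 5.1 | 2.8 | 5.3 | 4.9 |
| Unadjusted or footnote | 5.9 | 3.1 | 6.2 | 5.9 |
| Any of the three | 6.8 | 3.5 | 6.7 | 6.5 |
| Verdicts differ at 0.3, unadjusted v footnote, % | 5.5 | 5.1 | 6.4 | 6.5 |
| Verdicts differ at 0.3, text v footnote, % | 7.1 | 6.4 | 8.0 | 7.0 |
| Verdicts differ at 0.5, unadjusted v footnote, % | 5.7 | 5.9 | 2.2 | 1.9 |
| Verdicts differ at 0.5, text v footnote, % | 7.8 | 6.7 | 2.4 | 1.9 |
| SE, footnote list (food groups) | 0.211 | 0.203 | 0.141 | 0.140 |
| SE, footnote list + woreda, corrected | 0.214 | 0.174 | 0.143 | 0.138 |
| Power at 0.5 %, footnote list | 64.0 | 69.1 | 93.8 | 93.9 |
| Footnote list + woreda, corrected | 62.0 | 80.0 | 92.9 | 93.9 |
| Age + woreda, corrected | 61 | 78 | 92 | 95 |

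Uneven woredas (10,9,7,5 and 10,7,6) extend the null ranges slightly: single models 2.4% to 5.5%, any of three 3.5% to 7.2%. A smaller simulation under other assumptions (2,000 trials, 10 covariates explaining 15% of within-school variance) gave 6.0% to 7.4% for any of three at ICC 0.015.

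**4. Analytic check on woreda.** If a share s of the clustering lies between woredas, a woreda term gives DE = (1 − ICC) + 10 × ICC × (1 − s), with SE = 1.56√(2 × DE/270).

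- ICC 0.18: s = 0 gives DE 2.62, SE 0.217 and power 63% at 0.5; s = 0.5 gives DE 1.72, SE 0.176 and power 81%.
- ICC 0.015: DE 1.135 and 1.06; power 94% and 95%.

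**5. Adding woreda safely.** The usual clustered variance uses the factor 54/53. With the footnote list plus woreda it rejects a true null in 6.5% to 7.2% of trials at 53 df, and in 6.4% to 7.2% if only the df are cut to 46. There are eight school-level terms (intercept, arm, six woredas), so 54 − 8 = 46. Replacing 54/53 by 54/46 raises the SE by √(53/46) = 1.073. With 46 df this rejects 4.7% to 5.4% for the footnote list plus woreda, and 4.2% to 5.4% for age plus woreda.

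**The case against.** The open-ended wording can contain the footnote list, so the two statements need not contradict each other, and the footnote may be the text rule resolved. That stands: they are unreconciled, not incompatible. But the SAP does not make the link, and if it is the right one, the covariates came from observed data.

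The survey round is partly answered. Data are a panel only at school level (SAP 1.2), so covariate values for 540 girls can only be endline values. The round stays open only for judging which variables differ. The respondent is also partly answered: Protocol Table 4 lists food security under the parent questionnaire only, although Protocol 4.1.4 also puts the scale to the girl.

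Three stronger readings are tempting and unsupported.

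- A reader might infer that the loose rule inflates the false-positive rate. No single model as written does so materially, and omitting woreda makes the test conservative when woredas differ (2.4% to 2.8% in scenario B).
- A reader might infer that the t-test in SAP 3.2 is the selection rule. The SAP gives it no such role, so step 2 and the text-rule rows are conditional on that reading.
- A reader might infer, because SAP 1.2 reports the endline survey in the past tense, that outcomes were seen before the model was written. The tense does not show that.

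**Conclusion.** The point holds at modest size. SAP 3.3 leaves the adjusted model with two unreconciled descriptions, ranks neither column and omits the randomisation stratum.

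The choice among models raises the null rejection rate to at most about 7%, and changes the verdict in about 2% to 8% of trials at true effects of 0.3 to 0.5 food groups. The upper end at 0.5 comes from ICC 0.18; at ICC 0.015 it is about 2%.

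Omitting woreda changes the SE by only 0.002 to 0.003 food groups at ICC 0.015, or at ICC 0.18 with no clustering between woredas. It costs about 10 points of power at ICC 0.18 if half the clustering lies between woredas, a share the documents do not give. All simulated figures rest on the assumed covariate strength, covariate ICCs and woreda sizes. The textual finding does not.

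**What to change.** 1. In SAP 3.3, delete the clause that admits whatever variables turn out to differ between arms, and put one closed list in both the text and footnote 2.
2. Name one primary estimate for the dietary diversity score: the endline regression on arm, girl age and six woreda indicators, with school-clustered errors.
3. Report as sensitivity analyses the unadjusted model, and a model that adds household food security and wealth tertile from the endline parent questionnaire. Both are measured after randomisation, in an unblinded trial whose interventions reach parents and homes, so they should not sit in the deciding model.
4. With woreda in the model, specify a small-sample correction, for example the clustered variance scaled by 54/46 with 46 df. Other corrections would serve. Without one, the test rejects a true null in about 6% to 7% of trials.
5. State the date of this choice and whether endline outcome data had been seen.

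Optional: report balance in SAP 3.2 descriptively or with school clustering, with no role in covariate selection, and state that the SAP supersedes Protocol 4.4 on covariates.

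Cost: no new data. Woreda uses six school-level degrees of freedom, about 1 to 2 points of power if woredas do not differ. Moving food security and wealth out of the primary model costs little: in a paired run, power at 0.5 with and without them was 62.5 v 61.1, 79.8 v 78.9, 92.4 v 92.7 and 94.0 v 93.9% (A to D).

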Across SNNPR and Somali regions, A&T selected seven woredas (districts) as potential intervention areas on the basis of having adequate school access and infrastructure. Four woredas were selected in SNNPR and three woredas in Somali region. In Somali, woredas with more settled communities and less security issues were selected; fewer woredas were also selected, compared with SNNPR, as the communities are more homogenous. The list of study woredas and their corresponding total numbers of primary schools with grades 1-8 are presented in **Table 1**.

Table 1. Study woredas and total number of primary schools available

No.	Region	Zone	Woreda	Population	Kebeles	Primary Schools with grades 1-8
1	Somali	Fafan	Gursum	37,425	15	11
2		Fafan	Harawa	32,034	16	9
3		Fafan	Keberi Beyah	165,518	29	15
4	SNNPR	Gurage	Sodo	175,400	54	32
5		Gurage	Muhor Na Aklil	119,137	29	34
6		Silti	Dalocha	89,807	18	19
7		Kembata Tembaro	Doyo Gena	78,634	18	23

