## 2.6 Sample Size

The primary study sample is adolescent girls enrolled in primary school and aged 10-14 years (grades 4-8). The sample size was estimated based on current prevalence of the primary outcome, the expected change after intervention, power to detect those differences (80%), and level of significance ( $\alpha=0.05$ ). As the intervention was randomized at the cluster level (54 clusters) rather than the individual level, cluster effect was considered for sample size calculation.

We used the number of food groups from the A&T Phase 1 endline survey for SNNPR (mean: 3.26, SD: 1.40, categorized as 9 food groups; Arimond et al., 2010), assuming an intra-cluster correlation (ICC) of 0.18. We calculated that a minimum sample of 189 girls per group will be able to detect a minimum of 0.6 food group consumption increase. The sample size at endline will be rounded to 270 girls per group so that 10 girls per school (2 per grade) will be sampled. Based on baseline data, we observed a mean of 3.69, SD: 1.56, categorized as 10 food groups. Assuming an ICC of 0.015, we estimated that this sample size will detect a minimum difference of 0.5 food groups.

School principals, science teachers and HEWs responsible for providing nutrition education or facilitating other related activities/interventions will also be included in both baseline and endline surveys.

At baseline, a light data collection at schools and subsamples of adolescent girls and their parents will be conducted to assess comparability between study arms. At endline, the full samples of adolescent girls and their parents will be surveyed (including those who participated at baseline).

Thus, the overall study samples are presented in **Table 3**.

Table 3. Sample sizes

	Baseline 2019		Endline 2021	
	Intervention	Control	Intervention	Control
Adolescent girls	81	81	270	270
Parents of adolescents	81	81	270	270
Principals (1 per school)	27	27	27	27

Science teachers (1 per school)	27	27	27	27
HEWs (1 per school)	27	27	27	27
Total	243	243	621	621

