#### 3.3.1 Analysis of program impact pathways [RQ3]

In addition to the estimation of impacts, we will conduct plausibility analysis to provide further evidence for the likelihood or strength of our impact estimates, by examining the intermediate outcome indicators along the program impact pathways (from service delivery to exposure and behavioral

determinants) to determine whether the program resulted to the outcomes as intended by design. The program impact pathway (PIP) was developed in collaboration with the A&T program team to map out the mechanisms through which the interventions were expected to achieve impact. The purpose of the PIP analysis is to lay out the theoretical causal links between program activities, outcomes, and impacts. We will examine key indicators along the components of pathways (presented in RQ3), to interpret and support the impact evaluation results. We will compare differences between program groups for indicators along the pathway matched to the relevant outcomes, using linear regression models accounting for school clustering.

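### Schools were randomised within seven woredas, but no stated endline impact or pathway model includes woreda, so inference is conservative if woredas differ

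*SAP*

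**What the plan says.** The design is stratified. Protocol 3.1 states: "We will use stratified randomization within woreda to try to balance potential co-interventions and confounders". SAP 1.2 confirms that this was done: "We applied stratified random allocation to 54 primary schools within 7 districts".

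The analysis does not carry the strata forward. SAP 3.3 uses linear regression of the endline outcome on arm, with standard errors clustered by school. Table 6 defines two versions:

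- Unadjusted: "Controlling for clusters by school only".
- Adjusted: "Adjusted for AG age, household food security and wealth tertile, and clustered by school". The text above the table also allows "other variables that differed between study arms".

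The pathway comparisons in SAP 3.3.1 are made "using linear regression models accounting for school clustering". Protocol 4.4 describes a random-effects regression and DID or ANCOVA estimation, and names neither woreda nor region.

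**The concern.** When allocation is stratified, differences between strata largely cancel out of the arm contrast, so its true variance falls. A model that omits the strata leaves those differences in the residual, and the reported SE does not fall with the true one. Intervals are then wider than they need to be, and the real type I error lies below 5%.

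The open covariate rule does not close the gap. It selects variables that differ between arms, and stratification balances woreda by design, so the rule would normally pass over it.

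What is at stake is precision, not validity. There is also a question of timing: if woreda is not pre-specified, adding it after the data have been seen is a post hoc choice. The DID robustness check is not part of this point.

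**Working it through.** **The plan's own figure.** Protocol 2.6 gives SD 1.40, difference 0.6, ICC 0.18, 80% power, α = 0.05 and 54 schools (27 per arm). With a two-sided test:

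- Individual n = 2 × (1.960 + 0.842)² × 1.40² / 0.6² = 85.5 per arm.
- Girls per school = 85.5 × (1 − 0.18) / (27 − 85.5 × 0.18) = 6.03, rounded up to 7.
- 27 × 7 = 189, as stated.

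The update in the same section reads: "Assuming an ICC of 0.015, we estimated that this sample size will detect a minimum difference of 0.5 food groups". With SD 1.56 and 10 girls per school, (1.960 + 0.842) × 1.56 × √[(2/270)(1 + 9 × ICC)] is 0.40 at ICC 0.015 and 0.50 at ICC of about 0.085. For that reason 0.085 is included below as a sensitivity value.

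**Hand check of the mechanism.** With 27 schools per arm and 10 girls per school, the variance of the arm difference is (2/27) × SD² × [ICC + (1 − ICC)/10]. If a share s of the between-school variance lies between woredas, even stratification replaces ICC by ICC × (1 − s) in the true variance.

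- SD 1.40, ICC 0.18, s = 50%: the SE ignoring strata is √(2/27 × 1.96 × 0.262) = 0.195. The true SE is √(2/27 × 1.96 × 0.172) = 0.158.
- SD 1.56, ICC 0.015, s = 50%: √(2/27 × 2.4336 × 0.1135) = 0.143 against √(2/27 × 2.4336 × 0.106) = 0.138.

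The real gap is somewhat smaller. Both regional school totals (31 and 23) are odd, so at least one woreda per region cannot split evenly. In addition, with only seven woredas the residual picks up slightly less than the full woreda variance.

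**Simulation.** There were 6000 trials per scenario (8000 for the pathway case), two-sided α = 0.05, with 54 schools of 10 girls allocated 27:27 within woredas. Two things are assumed because the documents do not give them: the numbers of study schools per woreda (7/6/10 in Somali, 9/10/5/7 in SNNPR) and the woreda share. The model without woreda is arm only, with an ordinary school-clustered SE and 53 df. The model with woreda is a regression of school means on arm and six indicators, with 54 − 8 = 46 df.

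| SD, effect, ICC | Woreda share | Power without → with woreda |
|---|---|---|
| 1.56, 0.5, 0.015 (current inputs) | 0% | 93.4% → 92.7% |
| | 50% | 94.0% → 94.0% |
| | 100% | 94.9% → 95.9% |
| 1.40, 0.6, 0.18 (original inputs) | 0% | 86.2% → 85.2% |
| | 30% | 88.8% → 92.3% |
| | 50% | 90.4% → 95.9% |
| 1.56, 0.5, 0.05 (sensitivity) | 50% | 88.1% → 91.0% |
| 1.56, 0.5, 0.085 (sensitivity) | 50% | 83.5% → 88.5% |
| 1.56, 0.5, 0.18 (sensitivity) | 50% | 66.4% → 78.9% |

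Without woreda, at a 50% share:

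- Original inputs: reported SE 0.188, true SE 0.162, type I error 2.6%.
- SD 1.56, ICC 0.18: reported SE 0.209, true SE 0.180, type I error 2.7%.
- SD 1.56, ICC 0.085: type I error 3.0%.

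**Pathway models with one principal, teacher or HEW per school (27 versus 27).** The assumed difference is 0.8 SD. With 0%, 20% and 30% of total variance between woredas, power goes from 82.2% to 81.7%, from 85.7% to 89.5%, and from 86.7% to 92.0%. Type I error without woreda is 3.3% at 20% and 2.6% at 30%.

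**Second simulation.** With other assumed woreda sizes (8, 8, 7 and 8, 8, 8, 7), SD 1.56 and a 50% share, the ratio of reported to true SE without woreda was 1.12 at ICC 0.085 and 1.18 at ICC 0.18. At ICC 0.015 it never exceeded 1.03, and with no woreda variance it was about 1. A more uneven split gave the same pattern.

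**Choice of variance method.** Woreda indicators with the ordinary clustered SE and 53 df gave type I error of 6.1–7.1%. The school-means analysis with 46 df gave 4.6–5.3% in every scenario.

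**The case against.** The strongest reply is that the plan loses nothing it counted on. At the current ICC of 0.015, woreda makes no practical difference. At the original inputs the planned model has 86.2% power with no woreda variance and 90.4% at a 50% share, both above the 80% target. Power drops below 80% only when SD 1.56 and effect 0.5 are paired with ICC 0.18, a pairing the protocol does not use, and there adding woreda reaches only 78.9%. This stands: it is a gain not taken, not a shortfall.

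The between-woreda variance is also unknown. Regional contrasts in the protocol may overstate it, because "In Somali, woredas with more settled communities and less security issues were selected". This stands too, and the shares above are illustrative. On the other side, 0.015 is itself only an assumption, replacing 0.18.

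The simulations contain no covariates, so the impact figures describe the unadjusted column. Food security and wealth may absorb part of the woreda variance. If they absorbed half (an assumption), the gain at a 50% share would shrink to 93.9% → 95.8% at the original inputs and 85.5% → 87.6% at SD 1.56 and ICC 0.085. At 80% absorbed it would be under one point. This reduces the gain for the adjusted column but does not remove the reason to respect the strata.

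Last, the remedy changes the variance method, and school means alone cannot carry girl-level covariates. That is correct, but a workable route exists: a two-stage school-level analysis with a girl-level covariate gave type I error of about 5–6%. The random-effects alternative was not simulated.

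**Conclusion.** The point holds as a conditional one. If outcomes differ between woredas, the planned endline and pathway models report SEs that are too wide and tests that are conservative, with no bias and no inflation of false positives. At ICC 0.015 the effect is negligible. It becomes material if the endline ICC is nearer the 0.18 first assumed, or for pathway indicators that vary by woreda. At ICC 0.18 and a 50% woreda share, forgone power is 5.5 points at the original inputs (95.9 − 90.4) and 12.5 points at SD 1.56 and effect 0.5 (78.9 − 66.4). These sizes rest on assumed woreda shares, assumed numbers of schools per woreda, two-sided tests as in SAP 3.1, and no covariates. It is a worthwhile, low-cost improvement; confidence in its size is medium.

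**What to change.** - Pre-specify six woreda indicators in the unadjusted and adjusted endline impact models and in the pathway models.
- Base inference on the school level with 46 df. For the unadjusted model, regress school means on arm and woreda. For models with girl-level covariates, use a two-stage school-level analysis, or the protocol's random-effects regression with a small-sample df correction, checking its type I error by simulation first.
- Do not add the indicators while keeping the ordinary school-clustered SE.
- Amend both Table 6 footnotes to say that woreda is included.
- Report the between-woreda and within-woreda ICC.

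The SAP describes the endline survey as already conducted, and the documents do not show whether analysis has begun. Date the change; if outcomes by arm have been seen, label it post hoc and keep the planned model alongside.

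No new data are needed, since woreda is known for every school. The costs are a change of SAP wording, six degrees of freedom, a different variance method, and roughly 0.5 to 2 points of power if woredas do not differ.
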